Solid stars on diagram denote when doses of study vaccine may be administered. Stars with dashed outlines denote doses that may be withdrawn if the participant does not tolerate previous doses given.

Study vaccine will be administered in an observer-blind fashion. Participants will be followed for safety and immunogenicity through at least 56 days after last vaccination (which may entail total participation of up to Day 396 for participants, depending on the date of enrollment and the timing of last vaccination). At a subset of clinical sites, all enrolled participants will also undergo blood sampling for evaluation of CMI responses.

With protocol version 4.0, participants who wish to seek off-study COVID-19 vaccine will be allowed to continue with study participation. See Section 4.2.3.

With protocol version 6.0, the study is terminating as of a target date of 16 February 2022. Final visits will revert to Early Termination visits for all participants.

Vaccine doses will be assigned as shown in [Synopsis Table 1-1](#) and illustrated in [Synopsis Figure 1-2](#).

[figure not shown]
Synopsis Table 1-1 Study Group Assignments

Stratification Groups	Study Groups	Priming Vaccination 1 (Day 0) Randomized 1:1:1:1	Priming Vaccination 2 (Day 28)	Booster Vaccination (Day 208)		
				Booster randomization ratio: ARCT-021 : ARCT-154 : ARCT-165 : Placebo 1:1:1:1		
Younger adults ^a AND Older adults ^b	1	ARCT-021 7.5 µg	Placebo	ARCT-021 5.0 µg ARCT-154 5.0 µg ARCT-165 5.0 µg Placebo		
		2	ARCT-021 5.0 µg			
		3	ARCT-021 7.5 µg			
	4	Placebo	Placebo	If not re-enrolled at Day 98-198^c: Booster Vaccination (Day 208) Booster randomization ratio: ARCT-021 : ARCT-154 : ARCT-165 1:1:1 (No Placebo)		
				If re-enrolled (Day 98-198) Vaccination 1 (Day 0) Groups 1, 2, and 3 (No Placebo) Randomized 1:1:1	Vaccination 2 (Day 28)	Booster Vaccination (Day 208) 1:1:1:1 (Includes placebo)
				ARCT-021 7.5 µg	Placebo	Placebo ARCT-021 5.0 µg ARCT-154 5.0 µg ARCT-165 5.0 µg
				ARCT-021 5.0 µg	ARCT-021 5.0 µg	
				ARCT-021 7.5 µg	ARCT-021 7.5 µg	

^a Younger adults: 18 to <56 years of age in US and 21 to <56 years of age in Singapore

^b Older adults: ≥56 years of age

^c See Section 5.1

Synopsis Figure 1-2 Flowchart for Priming Vaccination, Re-Enrollment, and Booster Vaccination

A DSMB will be in place to independently review the safety data of participants. Pausing Rules are also utilized in this study to reduce risk to study participants.

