4.2.2 Discontinuation of Study Vaccine (Participant)

Additional administrations of study vaccine are absolutely contraindicated for any of the following reasons:

- Grade 3 solicited AEs (as confirmed by Investigator review), severe anaphylaxis, severe related (possibly, probably, or definitely) unsolicited AEs, or immediate type hypersensitivity (≤ 4 hours after injection) following the administration of the study vaccine.
- Any SAE judged to be related (possibly, probably, or definitely) to vaccine.
- Pregnancy in a female participant.
- Any clinically significant medical condition that, in the opinion of the Investigator, poses an additional risk to the participant if he/she continues to participate in the study.
- New information becomes available that makes further participation unsafe.

Arcturus Therapeutics, Inc.
Protocol ARCT-021-04, Version 6.0

ARCT-021
09 March 2022

A participant should not receive subsequent administrations of study vaccine for any of the following additional reasons:

- Participant receives an off-study COVID-19 vaccine
- Participant is lost to follow-up.
- As deemed necessary by the Investigator for non-compliance or other reasons. This may include previously undisclosed or new conditions that meet exclusion criteria.
- Termination of the trial.

If any of these events occur during the study, then the participant must not receive additional doses of study vaccine. Furthermore, the participant will be encouraged to continue study participation for safety and immunogenicity evaluations through the Early Termination Visit after the first vaccination.

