4.2.3 Withdrawal/Discontinuation From Study

Participants are free to withdraw from participation in the study at any time upon request, without any consequence.

A participant will be discontinued from the study if any of the following occur prior to first administration of study vaccine:

- The participant requests to discontinue study participation.
- Study vaccine is not administered.

A participant may withdraw from the study at any time at his/her own request. Reasons for discontinuation from the study may include the following:

- Refused further follow-up.
- Lost to follow-up.
- Death.
- Study terminated by the Sponsor.
- AEs.
- Participant request.
- Investigator request.
- Protocol deviation.
- Opportunity to receive an approved COVID-19 vaccine (with protocol version 4.0 participants who wish to seek off-study COVID-19 vaccine will be allowed to continue with study participation).

If a participant approaches the site requesting to receive off-study COVID-19 vaccine, the participant should be counseled and reminded of the study design allowing greater possibility of access to active study vaccine at either Day 98 or additional study vaccine at Day 208 (booster administration). The participant should be encouraged to demonstrate evidence of a scheduled appointment to receive off-study COVID-19 vaccine. If after counseling and

Arcturus Therapeutics, Inc.
Protocol ARCT-021-04, Version 6.0

ARCT-021
09 March 2022

confirmation of the appointment, a study participant maintains his/her interest in receiving off-study vaccine, he/she will be advised that the Sponsor and the site will not provide the off-study vaccine, the participant is advised to preferably schedule off-study vaccine at least 28 days after last dose of study vaccine, and the participant will not be eligible to receive additional doses of study vaccine. However, the participant is invited to continue study procedures through to Early Termination Visit.

For any participant terminating the study sooner than 60 days after last study vaccine administration, the following guidelines should be observed:

- The participant should also be reminded about use of highly effective contraception until 60 days following last study vaccine exposure.
- Any pregnancy occurring during this window should be reported to the Sponsor as soon as feasible.
- Should the PI/Site become aware at any time of any death or pregnancy occurring in these subjects it should be reported to Sponsor.

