Prior to the finalization of SAP Version 3.0, Arcturus Therapeutics had determined to early terminate the study prior to the planned visits up to Day 570. In notifications sent to the Singaporean Health Authority (HSA) and US Food and Drug Administration (FDA), it was specified that final study vaccinations would conclude in December 2021 and safety would be followed through 56 days after final vaccination or February 2022, whichever came first. This decision was taken based on refocusing development efforts on other COVID-19 vaccine candidates. However, it was also recognized that due to the study participation attrition, the significant risk of receipt of other COVID-19 vaccines by participants the study may be limited in its interpretation at timepoints beyond Day 56.

2. Study Objectives and Endpoints

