8.3.2. CMI Analysis

CMI responses will be evaluated for CMI subset using parametric flow cytometry for quantification and phenotyping and cytokine staining for TNF- α , IL-2, IFN- γ , IL-4, and IL-13. Blood sampling will be performed at Days 0, 14, 28, 42, 56, 208, 215, 236, and Early Termination in participants enrolled at centers identified with capabilities for isolation of peripheral blood mononuclear cells (PBMCs). CMI testing will not be performed on participants re-enrolling at Day 98-198 (i.e., placebo participants who re-enter the study to receive ARCT-021 priming vaccinations).

Descriptive statistics (N, mean, SD, min, Q1, median, Q3, max) will be provided for each visit including change from baseline at each timepoint, where CMI results are available for the priming vaccination period (mITT and PP analysis CMI subsets) and booster vaccination period (Booster mITT CMI subset). When summarizing the Early Termination visit, only include observations within the booster vaccination period post day 236. The following CMI responses will be summarized:

- CD4+ T-cell responses background subtracted (combined pools): IFN- γ , TNF- α , IL-2, IFN- γ + TNF- α +, IFN- γ + TNF- α + IL-2+
- CD8+ T-cell responses background subtracted (combined pools): IFN- γ , TNF- α , IL-2, IFN- γ + TNF- α +, IFN- γ + TNF- α + IL-2+

- Th1/Th2 CD4+ T-cell responses background subtracted (combined pools): IFN- γ , IL-4, IL-4+ IL-13+, IFN- γ + / IL4+ IL13+

Box plots will be provided for the following for priming vaccination period (mITT CMI subset): CD4+/CD8+ IFN γ , IL4+IL13+, IFN γ +/IL4+IL13+, Th1/Th2.

Analyses will be performed overall and by age group (younger adults (≥ 18 - < 56 years), older adults (≥ 56 years)) for priming vaccination period (mITT CMI subset).

Summary tables and figures will exclude any data points collected at or after the first occurrence of the following intercurrent events: death, missed second ARCT-021 (if applicable) dose, use of immune-modifying drugs, and study infection. Summary tables and figures will exclude all data from subjects with early (before Day 7), active or prior SARS-CoV-2 infection at first vaccination.

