13.5. Appendix 3: Estimands and Intercurrent Events

Possible intercurrent events are presented in the table below.

Table 13-3 **Intercurrent Event Types**

Label	Intercurrent Event Type
IcEv1 (Death)	Death due to any cause (including pneumonia) other than COVID-19.
IcEv2 (Missed dose)	Does not receive the second vaccination at Day 28 where second vaccination assigned was ARCT-021 or does not receive booster vaccination at Day 208 where booster vaccination assigned was active ARCT booster. It is not necessary to exclude placebo missed second doses as there is no impact.
IcEv3 (Immune-modifying)	Use of immune-modifying drugs or non-study vaccines which interfere with immunogenicity. Immune-modifying drugs will be determined from a medical review of medications taken during the study.
IcEv4 (Early infection)	
Priming vaccination period: Antigens or antibodies indicating exposure to SARS-CoV-2 prior to vaccination or early infection before Day 7. (This IcEv is particularly relevant to assessing immunogenicity.) Early infection is defined as follows:
 
 ○ Positive PCR saliva test at baseline OR ○ Positive PCR test at any time up to 7 days post-baseline OR ○ Positive SARS-CoV-2 baseline serostatus 
Booster vaccination period: Antigens or antibodies indicating exposure to SARS-CoV-2 prior to vaccination or early infection before Day 7 post booster vaccination. (This IcEv is particularly relevant to assessing immunogenicity.) Early infection for different boosters is defined as follows:
 
 ○ Positive PCR saliva test on Day 208 OR the booster vaccination OR ○ Positive PCR test at any time up to 7 days post-booster vaccination
IcEv5 (Study infection)	Develops COVID-19 or asymptomatic SARS-CoV-2 infection on or after Day 7. (This IcEv is particularly relevant to immunogenicity and CESI events.). Study infection is defined as COVID-19 infection recorded on the adverse event CRF page with start date on or after Day 7. The following AE preferred terms will be considered: Asymptomatic COVID-19, COVID-19, Suspected COVID-19. Positive MSD nucleocapsid antibody value of 5000 AU/mL or higher at any point after baseline (with start date on or after Day 7) will also be considered as on-study infection.

Attributes for the primary safety estimands with strategies for IcEvs are presented in Table 13-4 below.

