Estimand Label	Estimand 2 (Geometric Mean Titers/Concentrations)
Estimand Description	
The GMT of NAbs (primary) and BAbs (secondary) against SARS-CoV-2 up to Early Termination after first vaccination with ARCT-021 of each group (5.0, 7.5 µg, or placebo) and with/without booster dose in healthy adults.
 
Interest will lie in comparing the GMT of each dosing regimen to placebo based on the Geometric Mean Ratio (GMR).
 
The hypothetical strategy is used to estimate antibody levels had all scheduled vaccinations been received, and without subsequent SARS-CoV-2 infection or influence from immune-modifying drugs or non-study vaccines. The principal stratum strategy excludes those with active or early SARS-CoV-2 infection within 7 days after the first study vaccine administration.

Analysis Population	Vaccinated healthy adults (as defined by eligibility criteria) without active or early SARS-CoV-2 infection (infection within 7 days after the first vaccination).
Endpoint	Total NAbs (primary) and BAbs (secondary) specific for the SARS-CoV-2 measured pre- and post-priming vaccine administration (on Day 0, 14, 28, 42, 56, and 208) and following booster vaccine administration (Day 236, Early Termination).
Treatment Conditions	Placebo or 5.0 µg or 7.5 µg ARCT-021 administered on Day 0, Day 28; placebo, ARCT-021, ARCT-154, or ARCT-165 administered on Day 208.
Population-Level Summary	The GMT and GMR of comparisons of interest at each time point. GMR will compare responses in placebo-, ARCT-021-, ARCT-154-, and ARCT-165-vaccinated groups at relevant timepoints. For additional considerations on population-level summary see the SAP.
Intercurrent Event Strategy	
IcEv1 (Death)	Hypothetical strategy
IcEv2 (Missed dose)	Hypothetical strategy
IcEv3 (Immune-modifying)	Hypothetical strategy
IcEv4 (Early infection)	Principal stratum strategy (based on study phase)
IcEv5 (Study infection)	Hypothetical strategy
Rationale for Strategies	Hypothetical strategy is used to understand antibody levels achieved through receiving scheduled vaccination, without subsequent SARS-CoV-2 infection and without any influence from immune-modifying drugs or non-study vaccines. In estimation, the hypothetical uses a statistical model on the mITT (excluding data points following intercurrent events and not complete removal of all data for the participant).

Estimand Label	Estimand 3 (Rise/Seroconversion)

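### Read literally, the CMI exclusion list in SAP 8.3.2 is narrower than the intercurrent events in Table 13-3: it leaves out non-study vaccines and missed active boosters

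*SAP*

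**What the plan says.** SAP 8.3.2 has its own exclusion rule for CMI tables and figures. Values are removed from the first of four events onward: "death, missed second ARCT-021 (if applicable) dose, use of immune-modifying drugs, and study infection". A second sentence removes all data from participants infected early or before first vaccination.

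SAP Appendix 3, Table 13-3, defines the intercurrent events. IcEv3 reads "Use of immune-modifying drugs or non-study vaccines which interfere with immunogenicity". IcEv2 covers a missed ARCT-021 second dose and also the participant who "does not receive booster vaccination at Day 208 where booster vaccination assigned was active ARCT booster". Protocol Table 7-1 likewise includes non-study vaccines and missed boosters. For the antibody estimands, SAP Table 13-5 applies a hypothetical strategy to these events, "excluding data points following intercurrent events and not complete removal of all data for the participant".

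On off-study vaccination, Protocol 4.2.3 states that "with protocol version 4.0 participants who wish to seek off-study COVID-19 vaccine will be allowed to continue with study participation". Protocol 4.2.2 lists "Participant receives an off-study COVID-19 vaccine" among the reasons to give no further study vaccine. SAP Section 1 names attrition and then "the significant risk of receipt of other COVID-19 vaccines by participants the study may be limited in its interpretation at timepoints beyond Day 56".

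**The concern.** The CMI assay stimulates cells with spike peptide pools (Protocol Synopsis, Immunogenicity Assessments), and Protocol 1.3 describes the authorized vaccines as targeting spike. The assay therefore cannot tell a response to an off-study vaccine from a response to a study vaccine. If values taken after an off-study vaccine are kept, the summary for that group mixes the two.

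The exposure is foreseeable. CMI is sampled at Days 208, 215, 236 and Early Termination, well after participants could have been vaccinated elsewhere. At stake are the late CMI summaries by group, including the durability description in Protocol 7.6.5 and the booster-period results.

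**Working it through.** The plan states no figure on this point, so the check compares the texts and then traces who would be affected.

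**Step 1. The list against the definitions.**

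| Event | SAP 8.3.2 (CMI) | SAP Table 13-3 |
|---|---|---|
| IcEv1 | Death | Death from causes other than COVID-19 |
| IcEv2 | Missed ARCT-021 second dose | Missed ARCT-021 second dose, or missed assigned active booster |
| IcEv3 | Immune-modifying drugs | Immune-modifying drugs, or non-study vaccines |
| IcEv5 | Study infection | Study infection on or after Day 7 |

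The second half of IcEv2 and the second half of IcEv3 are absent from 8.3.2. SAP Section 11 records a change to the CMI objective but no change to the CMI exclusions. SAP Section 1 says the SAP takes precedence over the protocol, so Protocol Table 7-1 does not repair the gap.

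**Step 2. Would another rule catch these values?**

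- *Missed second dose.* This catches a participant vaccinated elsewhere before Day 28 who then misses an assigned ARCT-021 second dose. It does not catch anyone vaccinated elsewhere after completing priming.
- *Per-protocol set.* SAP 4.4.4 removes major deviations expected to affect immunogenicity, which may protect the priming PP-CMI summaries. It does not apply to mITT-CMI. For the booster period, SAP 4.4.14, 8.3.2 and 8.4 present CMI on Booster mITT-CMI only. SAP 5.1 counts a Booster PP-CMI subset, but no CMI analysis uses it.
- *Missed active booster, if it were added.* A participant who was never randomized to a booster had no active booster to miss. For that participant, only the non-study-vaccine half of IcEv3 would work.

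**Step 3. Where the values would land.** Day 208 before the booster belongs to the priming period (SAP 4.4), so retained values enter the priming group, placebo included. In the booster period, SAP 4.4.12 puts participants with data but no booster randomization into the placebo booster group, shown in Table 4-1 as H1 and H2. Participants randomized to an active booster but not dosed stay in their assigned arm. The documents do not say how many there are.

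**Step 4. Illustration on assumed values.** Let f be the share of a group vaccinated off-study, and k their mean response relative to the rest of the group. The documents give neither. The group mean is then multiplied by 1 + f(k − 1):

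- f = 10%: 1 + 0.1 × 1 = 1.1 for k = 2; 1 + 0.1 × 4 = 1.4 for k = 5
- f = 30%: 1.3 for k = 2; 2.2 for k = 5
- f = 50%: 1.5 for k = 2; 3.0 for k = 5

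This applies to means only. SAP 8.3.2 also reports medians and quartiles, which would move differently.

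**The case against.** The best defence is that 8.3.2 is shorthand. It speaks of intercurrent events, the SAP's defined term, and follows the order of Table 13-3. The SAP's own label for IcEv3 is just Immune-modifying, and Table 13-4 labels IcEv2 Missed second, although both definitions are wider. This has force: it cannot be asserted that the sponsor meant to keep these values, or that they will be kept. But the estimand text in Tables 13-5 and 13-6 names drugs and non-study vaccines as two separate items, and Table 13-3 ties the identification of immune-modifying drugs to a medical review of medications. A programmer could reasonably follow the words of 8.3.2, and nothing there points to Table 13-3.

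A second defence is that no CMI rule is contradicted. Table 13-3 defines events; exclusion comes from the strategies attached to each estimand. CMI has no estimand, and Estimand 1 keeps data after the same events. This stands. A reader might infer a breach of a CMI estimand, and there is none. What remains is an unexplained difference between the CMI list and the definitions of the events it names.

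A third defence concerns consequences. No hypothesis is tested (Protocol 7.2), and no CMI model or treatment-difference estimate is planned (SAP 8.4). Protocol 4.2.3 advises waiting preferably 28 days or more after the last study dose before an off-study vaccine, so priming results through Day 56 are little exposed where that advice is followed. This also stands and limits the point to late, descriptive summaries.

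**Conclusion.** The point holds as a clarification of minor severity. Taken literally, 8.3.2 retains CMI values after an off-study COVID-19 vaccine and after a missed active booster, and no rule for mITT-CMI or Booster mITT-CMI is certain to remove them. The likely effect is inflation of comparator results, mainly from Day 208 onward. Its size is unknown: the multipliers of 1.1 to 3.0 rest wholly on assumed values and are not estimates.

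Three stronger readings are tempting but unsupported:

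- *The booster arms are diluted.* Booster randomization is at Day 208 and off-study vaccinees should receive no further study doses, so dilution needs people randomized to an active booster and then not dosed. The documents do not give their number.
- *The vaccine contrast shrinks.* Values after an off-study vaccine could also be retained in active groups, so no net direction is established.
- *The SAP blames off-study vaccination alone for limited interpretation beyond Day 56.* It cites attrition as well.

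**What to change.** In SAP 8.3.2, replace the list with: *at or after the first IcEv1, IcEv2 (missed assigned ARCT-021 second dose or assigned active booster), IcEv3 (immune-modifying drugs or non-study vaccines) or IcEv5, as defined in Table 13-3.* If a narrower CMI rule is intended, say so and give the reason in SAP Section 11.

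The change is one sentence and needs no new data: Protocol 5.10.1 already has sites record non-study vaccinations throughout the study. The cost is fewer CMI values at Day 208 and later, in a subset drawn from only some sites.

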8.3.3. ACE2 Receptor Exploratory Analysis

Exploratory analysis of the following sVNT ACE2 receptor binding inhibition for three strains will be performed: VAC114_ECL_CoV-2_S, VAC114_ECL_CoV-2_S_B1.351, VAC114_ECL_CoV-2_S_B1.617.2. The analysis will be similar to the analysis specified for the primary and secondary immunogenicity endpoints (section 8.2.1) and will be performed for Priming (mITT analysis set) and Booster vaccination period (Booster mITT analysis set).

The LLOQ for each assay is shown below:

VAC114_ECL_CoV-2_S, VAC114_ECL_CoV-2_S_B1.351, and VAC114_ECL_CoV-2_S_B1.617.2: 0.78125 units/mL at the 1:10 dilution and 7.8125 units/mL at the 1:100 dilution

8.3.4. NAbs/BAbs Ratio Analysis

NAbs/BAbs ratio at each visit during priming vaccination period and booster vaccination period will be summarized using descriptive statistics by treatment group for the mITT and Booster mITT analysis sets, respectively. Binding antibody test results for both the spike protein and RBD will be included in this analysis. Neutralizing and binding antibody tests for two strains may be performed, but only NAbs/BAbs ratios derived from tests of the same strain of SARS-CoV-2 will be presented:

NAbs/BAbs Ratio	Parameter Codes	Analysis Period
Wuhan Neutralizing/Spike Binding	VAC62MN/VAC72S	Priming and Booster
Wuhan Neutralizing/RBD Binding	VAC62MN/VAC72R	Priming and Booster

Beta Neutralizing/Beta Spike Binding	VAC85MN/V83B1351	Booster Only
Beta Neutralizing/Beta RBD Binding	VAC85MN/VAC83RBD	Booster Only

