4.6. Missing Data Handling and Imputation Rules

No missing safety and reactogenicity results will be imputed. Incomplete AE onset and end dates will be imputed according to the rules specified in [Appendix 2](#). For safety analysis, percentages will be based on the analysis set of interest (e.g., Safety Set) within each treatment group and overall for the relevant vaccination/period of interest. For reactogenicity analysis, the denominator will be number of participants in the reactogenicity analysis set for the relevant vaccination/period of interest.

Any immunogenicity results that are below the limit of detection (LOD) or lower limit of quantification (LLOQ) will be imputed as half of the corresponding limit and results above the upper limit of quantification will be imputed as that limit for analysis purposes.

5. Participant Disposition and Protocol Deviations

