
- Seropositivity is defined as any detectable antibody level above the lower limit of quantification (LLOQ) for the specific assay and antibody measured.
- For the MesoScaleDiscovery nucleocapsid antibody test (VAC72_ECL_CoV-2_N), seroconversion will be assessed in 2 ways:
 - Defined as a 2- or 4-fold increase above baseline (pre-vaccination antibody levels).
 - Based on detection of an antibody level ≥ 5000 AU/mL, a threshold associated with evidence of SARS-CoV-2 clinical infection/viral exposure.
- For all other assays and antibodies, seroconversion will be defined as a 2- or 4-fold increase above baseline (pre-vaccination antibody levels).
- For seronegative individuals, one half of the value of the LLOQ will be calculated as the baseline antibody level

The LLOQs for each assay are shown below.

- VAC62_MN_CoV-2 (IU/mL): 7.8431372549
- VAC72_ECL_CoV-2_N (BAU/mL): 0.06372
- VAC72_ECL_CoV-2_RBD (BAU/mL): 0.5168

VAC72_ECL_CoV-2_S (BAU/mL): 0.20723 The GMT will be calculated using the following formula:

$$GMT = e^{\left\{ \frac{\sum_{i=1}^n \log_e(t_i)}{n} \right\}}$$

where t_1, t_2, \dots, t_n are observed immunogenicity titers for n participants.

The GMFR measures the changes in immunogenicity titers within participants. The GMFR will be calculated using the following formula:

$$GMFR = e^{\left\{ \frac{\sum_{i=1}^n \log_e \frac{v_{ij}}{v_{ik}}}{n} \right\}} = e^{\left\{ \frac{\sum_{i=1}^n (\log_e v_{ij} - \log_e v_{ik})}{n} \right\}}$$

where, for n participants, v_{ij} and v_{ik} are observed immunogenicity titers for participant i at time points j and $k=0$ (Baseline, Day 0).

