8.3. Exploratory Immunogenicity Analyses

8.3.1. Assays for Response to SARS-CoV-2 Variants

To address the exploratory immunogenicity objective to evaluate responses to SARS-CoV-2 variants, the binding antibody responses of ARCT-021/ARCT-154/ARCT-165 will be compared to placebo for the booster vaccination period. SARS-CoV-2 binding antibodies (BAbs) will be tested using an MSD multiplex assay which measures total immunoglobulin G (IgG) against the full-length spike, RBD and N antigens of the beta strain. Neutralizing antibodies against the beta strain of SARS-CoV-2 will also be measured:

- IgG measured against the Nucleocapsid (N) antigen of the beta variant (B1.351) of SARS-CoV-2 (VAC83_ECL_CoV-2_N)
- IgG measured against the RBD antigen of the beta variant (B1.351) of SARS-CoV-2 (VAC83_ECL_CoV-2_RBD)

- IgG measured against the Spike antigen of the beta variant (B.1.351) of SARS-CoV-2 (VAC83_ECL-CoV-2_S_B.1.351)
- Microneutralization antibody concentration against the beta variant (B.1.351) of SARS-CoV-2 (VAC85_MN_CoV-2)

Similar estimands will be used as for the secondary objective.

The LLOQ for each assay is shown below:

- VAC83_ECL_CoV-2_N (AU/mL; 1:500 dilution): 27
- VAC83_ECL_CoV-2_RBD (AU/mL; 1:500 dilution): 19
- VAC83_ECL_CoV-2_S_B.1.351 (AU/mL; 1:500 dilution): 18
- VAC85_MN_CoV-2 (AU/mL; 1:5 dilution): 14

Assays for other variants may be analyzed as available as part of the exploratory analysis.

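### In SAP 8.3.4 the NAb/BAb ratio of a sample below LLOQ on both assays is set by the assay limits alone (37.85 for Wuhan spike), so baseline and unvaccinated placebo rows can exceed those of vaccinated responders

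*SAP*

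**What the plan says.** SAP 8.3.4 plans the ratio for the mITT and Booster mITT sets: "NAbs/BAbs ratio at each visit during priming vaccination period and booster vaccination period will be summarized using descriptive statistics by treatment group". Wuhan spike and RBD ratios are covered in both periods, beta spike and RBD ratios in the booster period only. The section has no rule for a component below the limit and does not name a geometric summary. The SAP Section 4 default for continuous variables is mean, median, SD, minimum and maximum.

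The handling of low results is in SAP 4.6: "results that are below the limit of detection (LOD) or lower limit of quantification (LLOQ) will be imputed as half of the corresponding limit". Derived ratios are not exempt. SAP 8.2.1 adds for baseline: "For seronegative individuals, one half of the value of the LLOQ will be calculated as the baseline antibody level".

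The Wuhan limits in SAP 8.2.1 are "VAC62_MN_CoV-2 (IU/mL): 7.8431372549" for neutralization, "VAC72_ECL_CoV-2_S (BAU/mL): 0.20723" for spike and "VAC72_ECL_CoV-2_RBD (BAU/mL): 0.5168" for RBD. SAP 8.3.1 lists the beta limits, including "VAC85_MN_CoV-2 (AU/mL; 1:5 dilution): 14" for neutralization, with 18 AU/mL for spike and 19 AU/mL for RBD, both at 1:500 dilution.

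mITT (SAP 4.4.3) requires valid, evaluable results, not results above LLOQ. Placebo is priming group D in SAP Table 4-1. Baseline is a priming time point and pre-booster Day 208 a booster time point in SAP 8.2.1. SAP Section 11 puts NAb in the numerator because neutralizing antibodies are regarded as part of the binding antibodies.

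**The concern.** A NAb/BAb ratio is naturally read as neutralizing activity per unit of binding antibody. That reading needs a denominator that was measured. When both components are imputed, the two halves cancel and only the quotient of the assay limits is left. In Wuhan units the neutralization limit is far above either binding limit, so this quotient is large.

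The rows where double imputation is most plausible, baseline and placebo before any active dose, could then show high Wuhan ratios. Vaccinated participants whose binding rises proportionally more than their neutralization would show lower ones. A reader of the table could not tell absent antibody from strongly neutralizing antibody. What is at stake is the interpretability of one exploratory output, which SAP Table 2-3 lists among the booster immunogenicity endpoints and SAP 8.3.4 also tabulates for priming.

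**Working it through.** The documents state no value for the ratio, so there is no plan figure to reproduce. All inputs are the LLOQs in SAP 8.2.1 and 8.3.1.

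**Both results below LLOQ.** Ratio = (LLOQ_NAb/2)/(LLOQ_BAb/2) = LLOQ_NAb/LLOQ_BAb.
- Wuhan spike: 3.9216/0.1036 = 7.8431/0.20723 = 37.85
- Wuhan RBD: 7.8431/0.5168 = 15.18
- Beta spike: 14/18 = 0.78
- Beta RBD: 14/19 = 0.74

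If the beta limits must still be multiplied by their dilutions (assumption), the last two become (14×5)/(18×500) = 0.0078 and (14×5)/(19×500) = 0.0074.

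**If LOD/2 applies.** No LODs are given. If each LOD lies between 0.5 and 1 times its LLOQ (assumption), the Wuhan spike value runs from 37.85×0.5 = 18.9 to 37.85/0.5 = 75.7.

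**What a responder needs to match it.** At spike 100 BAU/mL, NAb must be 100 × 37.85, or about 3,785 IU/mL.

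**Direction after vaccination.** For a participant starting below both limits, ratio = 37.85 × (NAb fold rise / spike fold rise), with rises taken from the imputed baselines:

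| NAb rise | Spike rise | Ratio |
|---|---|---|
| 4 | 20 | 7.6 |
| 10 | 100 | 3.8 |
| 20 | 500 | 1.5 |
| 100 | 50 | 75.7 |

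The ratio falls below the double-negative value only when spike rises proportionally more than NAb.

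**Only NAb below LLOQ.** Ratio = 3.9216/spike: 18.9 at the spike LLOQ, 3.9 at 1 BAU/mL, 0.39 at 10, 0.039 at 100 and 0.0078 at 500. The true ratio lies below 7.8431/spike, which at 500 is 0.0157, so a low value here is in the right direction.

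**Effect on a summary (illustration, not a forecast).** Take 75 participants, 60 with a measured ratio of 1 and 15 doubly imputed. The arithmetic mean is (15×37.85 + 60)/75 = 8.4 and the geometric mean is 37.85^(15/75) = 2.1, against 1.0 for both without the imputed values. If all 75 are doubly imputed, both means are 37.85.

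**The case against.** The strongest reply is that the size of the problem is assumed.

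- **Frequency.** A reader might infer that most baseline and placebo samples sit below both limits because infected participants are removed. The documents do not support that. The infection rules in SAP Appendix 3 rest on PCR and on nucleocapsid antibody at 5000 AU/mL or more, which does not imply spike or RBD below LLOQ. No baseline distribution is given. With NAb below LLOQ, a spike background of 1 BAU/mL already gives 3.9 instead of 37.85. SAP 8.3.4 also does not repeat the infection exclusion that SAP 8.3.2 states for CMI. This objection stands.
- **Differences between arms.** A reader might infer that these would mostly reflect the proportion below LLOQ. That is unsupported. Protocol 1.6 reports at least 4-fold spike seroconversion in more than 90% of participants after a single 5 µg dose, so double negatives should be uncommon in active arms soon after dosing.
- **Meaning of a high ratio.** The SAP never calls a higher ratio better, and IU/mL over BAU/mL has no direct absolute meaning. It proposes no Wuhan-against-beta comparison, and the beta double-negative values are below 1, so an inversion need not arise there.
- **Visibility.** A row of imputed constants would show median, minimum and maximum all equal, and seropositivity is tabulated by visit and arm. An attentive reader could notice. This helps with a row that is entirely imputed, but much less with a mixed one.
- **Consequence.** Protocol 7.2 has no hypothesis testing, and Protocol 7.8 records the Phase 3 dose as already selected. No primary, secondary or dose conclusion depends on this table.

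None of this removes the defect: the stated rules assign a specific value to a ratio that was not observed.

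**Conclusion.** The point holds for the mechanism and for what it can do. Under SAP 4.6 and 8.3.4 together, a sample below LLOQ on both assays contributes a constant: 37.85 for Wuhan spike, 15.18 for Wuhan RBD, and about 0.78 and 0.74 for beta without dilution scaling. The figures assume that LLOQ/2 is applied to both components; LOD/2 would give other constants, equally uninformative. For the Wuhan ratios, baseline and unvaccinated placebo rows can exceed those of vaccinated responders.

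A reader might go further and conclude that vaccination will appear to lower antibody quality. That is possible, not certain: it depends on an unknown share of double-negative samples and on binding rising proportionally more than neutralization. The analysis is exploratory and descriptive. The change is worth making because it is cheap and the affected cells cannot otherwise be interpreted.

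**What to change.** In SAP 8.3.4:

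1. Compute the ratio only for participant-visits with the binding result at or above its LLOQ.
2. Keep samples with BAb at or above LLOQ and NAb below LLOQ, flagged as imputed, noting that the true ratio lies below LLOQ_NAb/BAb.
3. Summarize by the median and the geometric mean ratio with 95% CI.
4. Report by arm and visit the number and percent excluded for BAb below LLOQ and the number and percent with NAb imputed.
5. Show the subset with both results quantifiable only as a supplementary row.

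Requiring both results to be quantifiable in the main row is tempting but should be avoided. It drops participants with high binding and no measurable neutralization, whose low ratio is informative, and so selects on response.

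The cost is a short addition to SAP 8.3.4 and a filter, a flag and count columns in the ratio tables. Baseline and placebo cells will become small or empty. Some limit-driven values remain: a flagged ratio with spike just at LLOQ can still be 18.9, and one with RBD just at LLOQ 3.9216/0.5168 = 7.6, which is why the imputed counts need to be shown.
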